4.2.8.4. Transvaginal Ultrasound

If the depth recorded for a TVUS of uterus is 0 mm, the depth and the volume should be considered as missing (i.e., this means that the assessment was done in 2 dimensions instead of 3 dimensions).

4.2.8.5. Partial and Missing Dates of diagnosis

For partial date of first medical diagnosis/treatment, first surgical diagnosis and most recent surgical diagnosis the following rules of imputation will be applied:

- If only Day is missing, Day will be imputed to 01.
- If Day and Month are missing:
 - if Year is the same as the screening date, Date will be imputed to Screening Date.
 - Otherwise, Day will be imputed to 01 and Month will be imputed to 07.
- If Date is completely missing, no imputation will be done.

4.2.9. Visit Windows

For all analyses except for the DXA assessments and the diary questionnaires, the visits as collected in the eCRF will be used.

E-diary questionnaires:

For diary questionnaires (EHP-30, EQ-5D-5L, HRPQ, HRUQ, PGIC, PPGIC, PGIS, PROMIS, SSIQ) except for the PSIQ, the e-diary dates of assessment of each visit will be checked versus the dates of same visit in eCRF to handle for e-diary visit errors. Only assessments within the window of the date of eCRF+/-14 days will be used in analyses. For Day 1 assessments, only data prior to the first dose will be used, regardless of the questionnaire visit name. In case of multiple assessments falling within the same window of an eCRF date, the non-empty record with completion date closest to the eCRF date will be used.

For data from discontinued visits, the discontinuation visit date should be compared to theoretical visit dates. Only assessments within the window of theoretical date +/-14 days will be used for analyses, if it is planned to have a such assessment at this visit and no other assessment is in the window. If a subject discontinued in the main treatment period, date will be compared to the theoretical visit dates in main treatment period as described in Table 3. If a subject discontinued in the follow-up period, date will be compared to the theoretical visit dates from Table 4. Note that assessments from

Sponsor:	ObsEva		
Protocol:	18-OBE2109-003		
Document Version No.:	V5.0		

discontinued visits in **Exercise** eDiary device are entered under Month 6 (Month 6 FU in follow-up). They will be recoded as discontinued visits before applying the windowing rules.

Table 3 Theoretical Visit Dates in Main Treatment Period

Visit	Theoretical Date
Month 1	Day 29
Month 2	Day 57
Month 3	Day 85
Month 4	Day 113
Month 5	Day 141
Month 6	Day 169

Table 4 Theoretical Visit Dates in Follow-up

Visit	Theoretical Date
Month 1 FU	Month 6 date or treatment discontinuation date + 28
Month 2 FU	Month 6 date or treatment discontinuation date + 56
Month 3 FU	Month 6 date or treatment discontinuation date + 84
Month 4 FU	Month 6 date or treatment discontinuation date + 112
Month 5 FU	Month 6 date or treatment discontinuation date + 140
Month 6 FU	Month 6 date or treatment discontinuation date + 168

Pharmacokinetics data:

Visit windows rules for PK data will be the following:

CRS-BS-TP-000005 V 1.0

Page 47 of 127

Cytel Confidential: This is a controlled document and shall not be changed, saved, copied or reproduced by any unauthorized

Sponsor:	ObsEva		
Protocol:	18-OBE2109-003		
Document Version No.:	V5.0	Document Date:	13-JUN-2022

- At day 1: PK assessment will be included in analysis if PK sampling is done >=1.5 hours after the dose and on the same day as Day 1.
- At other visits: PK assessments will be included in analysis if:
 - Assessment is Pre-dose (or PK time = dose time), or IMP intake is not done on the day of PK sampling (i.e. considered as pre-dose), and,
 - PK assessment date is within +/-10 days of the theoretical visit and up to 2 days after last IMP intake for Month 6 visit.

If the PK sampling time is missing, or the IMP intake on the same day is done and the IMP intake time is missing then assessments will not be included.

IMP intake status (done/not done) and IMP intake time from the Pharmacokinetics eCRF page will be used.

DXA data:

Visit windows rules for DXA assessments will be the following:

- The baseline DXA assessment will be derived as the latest non-missing DXA assessment with acceptable quality (accepted="Yes") prior to the baseline visit or the first non-missing assessment with acceptable quality (accepted="Yes") done up to 10 days after the baseline visit if there is no assessment prior to baseline..
- The DXA assessment at Month 6 will be derived as the first non-missing DXA assessment with acceptable quality (accepted="Yes") and dated between Month 6 theoretical date (=Day 169) 28 days and Month 6 theoretical date + 28 days.
- The DXA assessment at Month 6 Follow-Up will be derived in the same way as the DXA assessment at Month 6. Theoretical date of Month 6 Follow-up is 168 days after Month 6 theoretical date or after treatment discontinuation.

Other Safety Data:

Endometrial biopsy Screening window will include any assessment done prior to the first dose.

For other safety data, data from early discontinuation should be compared to theoretical visits dates. Only assessments within the window of theoretical date +/-14 days will be used for analyses, if it is planned to have a such assessment at this visit and no other assessment is in the window. If a subject discontinued in the main treatment period, date will be compared to the theoretical visit dates in main treatment period as described in Table 3. If a subject discontinued in the follow-up period, date will be compared to the theoretical visit dates in Follow-up period from Table 4. For unscheduled safety assessments, if the unscheduled assessment occurs in a window of +/-14 days of a planned eCRF visit for

Sponsor:	ObsEva			
Protocol:	18-OBE2109-00	18-OBE2109-003		
Document Version No.:	V5.0	Document Date:	13-JUN-2022	

which it was planned per protocol to have such assessment, and no assessment was done for that visit, the unscheduled assessment will be assigned to that visit. If an unscheduled assessment is equally distant from two eCRF visits with no corresponding safety assessment, the unscheduled assessment will be assigned to the next visit.

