8 STUDY DESIGN

This is a prospective, randomized, double-blind, placebo-controlled study to demonstrate the efficacy and safety of linzagolix administered orally once daily at doses of 75 mg alone and 200 mg in combination with low dose ABT (E2 1 mg/NETA 0.5 mg) versus placebo in the management of moderate to severe EAP in women with surgically confirmed endometriosis.

The study starts with an approximately 3-month screening period during which subjects will receive no study drug. Eligibility will be confirmed based on data collected during the screening period. After randomization, a 6-month Treatment Period will follow. Subjects will be randomized to one of the three treatment groups:

1. Linzagolix 75 mg
2. Linzagolix 200 mg combined with ABT
3. Placebo

Randomization will be conducted via an interactive web response system (IWRS) in a 1:1:1 ratio. There will be no stratification.

At 6 months, BMD change will be assessed via DXA measurement. Eligible subjects who have completed the 6-month treatment period may enter a separate extension study for 6 additional months of active treatment (no placebo control). In this extension study, subjects who previously received placebo will be randomly switched to one of the two active treatments (75 mg alone or 200 mg + ABT). Subjects who received active treatment will continue with the same treatment.

Subjects who decline to participate to or do not qualify for the extension study and who were exposed to at least 3 months of treatment will enter a 6-month drug-free follow-up. At the end of the 6-month follow-up period, subjects with a BMD decrease from baseline of >1.5% for lumbar spine and/or >2.5% for total hip will have an additional DXA scan 6 months later. Subjects who discontinue treatment prior to Month 3 will not enter the follow-up period.

The main analysis will be performed after 6 months of treatment and will include all of the subjects' data up to Month 6.

The study will last on average 15 months; 3-month Screening Period, 6-month Treatment Period and 6-month Follow-up (with 1 month being defined as 28 days/4 weeks). The duration excludes any washout period.

It is expected that only few subjects will have to enter the second 6-month follow-up period to have a DXA scan.

A schematic of the study design is shown in Figure 1.

[figure not shown]

Figure 1 : Study design

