5. CHANGES TO PLANNED ANALYSES

The following change to the protocol-defined statistical analyses is presented in this statistical analysis plan:

For secondary endpoints of change from baseline to Month 6 that are collected daily using the eDiary, the protocol states (Sections 13.5.3.1, 13.5.3.2, 13.5.3.3, 13.5.3.5, 13.5.3.6, 13.5.4) that the endpoints will be based on the 28 calendar days immediately prior to and including the day of the Month 6 visit (or the 28 calendar days immediately prior to and including the last dose date for subjects who discontinue treatment prior to Month 6).

In this SAP this definition has been modified to not include the Month 6 day, as for subjects entering the Extension Study, the Extension Treatment is received at Month 6 (i.e., on the Month 6 day), and for subjects entering the Main Study Follow-up, no treatment is received at Month 6 (i.e., on the Month 6 day).

The end of the 28-day period prior to Month 6 is defined in Section 4.2.11 as the last treatment administration date in the Main Study.

The following endpoints are impacted:

- Ranked Secondary Endpoints:
 - Change from baseline to Month 6 in DYS (VRS) and in NMPP (VRS) (Section 4.6.3.1)
 - Change from baseline to Month 6 in dyschezia (NRS) (Section 4.6.3.2)
 - Change from baseline to Month 6 in overall pelvic pain (NRS) (Section 4.6.3.3)
 - Change from baseline to Month 6 in dyspareunia (VRS) (Section 4.6.3.5)
 - No analgesics use/ no opiate use for EAP during the preceding 4-week period at Month 6 (Section 4.6.3.6)
- Additional Secondary Endpoints (Section 4.6.4): endpoints based on daily e-Diary entries

Updates from SAP Amendments since SAP V1.0 are summarized in the table below:

Sponsor:	ObsEva		
Protocol:	18-OBE2109-003		
Document Version No.:	V5.0	Document Date:	13-JUN-2022

SAP Version	Update description	SAP Section	Reason
V2.0	Addition of MCT analysis using Month 6 data for ranked secondary endpoints-Addition of corresponding M6 threshold analysis population-Addition of random sample for Month 6 MCT (N=200)-Clarification of blinding/unblinding process for M6-For threshold analysis population at Month 3, available anchor data needed among PGIC or PGIS or DYSME or NMPP only (since only the primary endpoint MCT are assessed at Month 3)	Section 3.1 Section 4.6.1 Section 4.3	FDA Advice/Information request Dated 16Aug2021 (Comment 14a)

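### The Month 6 questionnaire and DXA windows have no cut at the first extension dose, so a late record from a placebo woman already switched to linzagolix can count as a placebo Month 6 value

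*SAP*

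**What the plan says.** SAP 4.2.9 compares each questionnaire's diary date with the eCRF date of the same visit: "Only assessments within the window of the date of eCRF+/-14 days will be used in analyses". If several records qualify, "the non-empty record with completion date closest to the eCRF date will be used". The rule covers EHP-30, EQ-5D-5L, HRPQ, HRUQ, PGIC, PGIS, PROMIS and SSIQ. For DXA, the Month 6 value is the first accepted scan from 28 days before Day 169 to the upper limit, given as "and Month 6 theoretical date + 28 days".

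Other parts of the plan fix when randomized treatment ends. Protocol 11.2 has the last main-study dose on the day before the Month 6 visit. SAP section 5 changes the diary windows "as for subjects entering the Extension Study, the Extension Treatment is received at Month 6". Protocol section 8 states that in the extension "subjects who previously received placebo will be randomly switched to one of the two active treatments", while women on linzagolix keep their arm.

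Elsewhere in the SAP, dosing dates do set limits:
- Baseline questionnaires: "For Day 1 assessments, only data prior to the first dose will be used, regardless of the questionnaire visit name".
- PK samples: "up to 2 days after last IMP intake for Month 6 visit".
- Daily-diary endpoints at Month 6 end at the last main-study dose (4.2.11 and section 5).
- Appendix E uses the first extension intake as the cut-off when it remaps extension entrants' diary data.

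**The concern.** The Month 6 questionnaire and DXA rules mention neither the last main-study dose nor the first extension dose, and 4.2.11 keeps Month 6 by-visit assessments in the main study without a date limit. A record completed after a placebo woman has started linzagolix can therefore enter the analysis under her randomized label.

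For EHP-30 pain this clashes with SAP 4.6.3.4 (and Protocol 13.5.3.4), which ties the Month 6 value to the final four weeks on randomized treatment. The endpoint is fifth in the fixed sequence. A diluted result there could also block endpoints six to eight: dyspareunia, no analgesic use and no opiate use.

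For BMD the direction matters more. Linzagolix exposure in placebo women would lower the placebo mean and so understate bone loss attributable to drug. That is not conservative for a safety comparison.

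**Working it through.** **Plan figures.** The plan gives no count of late records and no estimate of the windows' effect, so there is nothing of that kind to reproduce. Its co-primary power (above 95%) does reproduce. With 150 per arm and two-sided alpha 0.025, NMPP at 18.8% versus 42.1% gives 0.987, DYS is above 0.9999, and joint power is 0.987 if the two are independent. Those endpoints are at Month 3 and are not touched. The 85% for the ranked secondaries cannot be reproduced because its means and SDs are not given.

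**Exposure permitted, questionnaires.** The first extension dose is on visit day V and the latest accepted record is V + 14. EHP-30 and mPGIS recall four weeks, so at most 14/28 = 50% of the recall can fall after the switch. Shorter recalls are more exposed. PROMIS and HRPQ ask about the past week and EQ-5D-5L about the same day, so a record 8 to 14 days late may reflect no randomized treatment at all.

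**Exposure permitted, DXA.** The window runs from 169 − 28 = Day 141 to 169 + 28 = Day 197. It is anchored on the theoretical day, so exposure is 197 − V:
- V = 172 (latest in-window visit): 25 days
- V = 169: 28 days
- V = 166 (earliest in-window visit): 31 days

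**Dilution of EHP-30 (assumption).** Let f be the share of placebo values recorded after the switch and g the share of the drug effect already present in them. The contrast is multiplied by 1 − f·g.
- f = 5%, g = 0.25: 0.05 × 0.25 = 1.25% smaller
- f = 15%, g = 0.50: 0.15 × 0.50 = 7.5% smaller

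As an illustration, take one endpoint with 85% power at alpha 0.025. The non-centrality is 2.241 + 1.036 = 3.278, and power after dilution is Φ(3.278 × (1 − f·g) − 2.241). With g = 0.5:
- f = 5%: 83.0%
- f = 10%: 80.9%
- f = 20%: 76.1%

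The plan's 85% is for the whole sequence, so under its own assumptions any single endpoint has at least that power. The starting point is therefore pessimistic.

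**BMD (assumption).** Protocol 5.5.3 gives −0.8% at the spine over 24 weeks (168 days) for 75 mg. If loss is linear and all due to drug, 31 days gives 0.8 × 31/168 = 0.148 percentage points per affected woman. The shift in the placebo mean is f × 0.148:
- f = 5%: 0.007 points
- f = 20%: 0.030 points

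At the 200 mg rate without add-back (−2.602%, Protocol 5.6), which the extension does not use, the same sums give 0.024 to 0.096 points.

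**The case against.** The best defence is that late values should be rare. The questionnaire window is there to catch visit-labelling errors in the diary, and among several records the one nearest the visit is taken. Protocol 10.2.2.5 plans the questionnaires ideally ahead of other procedures at the visit, and 10.3 provides a back-up device. For DXA, the scan may be done up to 10 days before the visit, its result bears on extension eligibility, and the first accepted scan is used. When a scan is repeated because of a loss of 5% or more, SAP 4.8.3 uses the initial one. All of this stands, and it limits the problem mainly to a record that is the only usable one. It does not close the gap: Appendix E itself describes Month 6 transition errors from remote visits and site mistakes, and results at the visit are only hoped for, not required.

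A reader might infer three stronger things that the documents do not support:
- That nothing in the plan confines these records to randomized treatment. For EHP-30, SAP 4.6.3.4 and Protocol 13.5.3.4 do. The fault is that 4.2.9 does not carry the definition out.
- That a scan repeated for poor quality will usually fall after extension dosing has begun. It may, but that depends on the extension protocol and imaging manual, which are not among the documents.
- That the PK limit of two days after last intake should also be applied to women who do not enter the extension. It is a plasma-concentration rule with no stated rationale for a four-week recall, and it could discard a questionnaire from a proper visit or discontinuation visit.

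**Conclusion.** The gap is real and narrow. The windows permit up to 14 days of active drug behind a placebo questionnaire and, for an in-window visit, up to 25 to 31 days behind a placebo scan. That contradicts the SAP's EHP-30 definition and its own treatment of diary data.

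The practical effect is unknown, because the number of late records is not given, and it is probably small. All dilution and power figures above rest on assumed f and g. A late EHP-30 record works against linzagolix, so there is no risk of a false efficacy claim from this route. The BMD bias runs the other way for safety. One might infer that it could hide a difference in bone loss, but a shift of 0.007 to 0.03 points at the 75 mg rate does not support that. The Month 3 co-primary endpoints and all daily-diary endpoints are unaffected. This is an inexpensive improvement, not a threat to the trial's conclusions.

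**What to change.** In SAP 4.2.9, for women who enter the extension (all arms alike), use only Month 6 questionnaires completed on or before the first extension dose, and pre-dose if on the same day. Report by arm how many records this excludes; that count alone would show whether the issue matters. State how the excluded values are handled, because 4.2.8.1 could be read as giving them a change of zero, which would bring a bias of its own. Leave the rule unchanged for women who do not enter the extension.

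Version 5.0 follows the version that added the Month 6 thresholds, after which section 4.3 lets unblinded results reach the sponsor. If the data are already unblinded, keep the current window for the main analysis and report the restricted one as a labelled sensitivity analysis.

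For DXA, repeat the Month 6 BMD ANCOVA without scans dated after the first extension dose.

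The cost is one date condition, some wording and one repeated model. The first extension dose date is already used in 4.2.8.2 and Appendix E. The downside is that a few late records become missing.

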5.5.1 Pharmacokinetics/Pharmacodynamics

Linzagolix was evaluated in a Phase 1 single/repeated-dose study (Study KLH1101) in which Japanese and Caucasian pre- and post-menopausal women received single doses of linzagolix from 12.5 to 700 mg and repeated once daily doses of 100 to 400 mg once daily for 7 days under fed and fasted conditions. Linzagolix was safe and well-tolerated, showed linear PK, a half-life of about 15–20 hours, and little difference between pre- and post-menopausal women or between Japanese and Caucasian women. There was a dose-dependent suppression of luteinizing hormone (LH), follicle-stimulating hormone (FSH) and E2.

Study 17-OBE2109-001 evaluated the tolerability and PK of a single supra-therapeutic dose of 700 mg linzagolix, and effects of therapeutic and suprathreshold doses of linzagolix on the QTc interval (QT interval corrected for heart rate). Subjects received a 200 mg dose of linzagolix (therapeutic target

exposure), a 700 mg dose of linzagolix (supratherapeutic target exposure), a 400 mg dose of moxifloxacin (positive control), and placebo with an appropriate washout. Linzagolix at 700 mg was well tolerated. A borderline effect of linzagolix on the heart rate corrected QT interval was identified with prolongations exceeding the threshold of concern by less than 2 msec. The categorical data for QTc showed no values greater than 480 msec and no changes greater than 30 msec following administration of the supratherapeutic and therapeutic doses. Thus, based on the magnitude of the QTc prolongation, the observed effects are not considered to be clinically significant.

The open-label study, KLH1103, assessed the absorption, metabolism, and excretion of linzagolix in 6 women of non-childbearing potential. Linzagolix was the predominant component in plasma and all plasma metabolites were present at less than 10% of the total drug related exposure. Similarly, unchanged linzagolix was also a major component in urine and feces. Linzagolix was eliminated in urine (52%) and, to a lesser extent, in feces (38%).

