10.5 LINZAGOLIX AND KP017 PLASMA LEVELS

PK blood samples will be collected from each subject for determining linzagolix and KP017 plasma levels.

On Day 1, blood samples for PK assessment will be taken at least 1.5 h post-first dose.

During the treatment period, on days of site visits at Months 1, 2, 3, 4 and 5), the subject will be asked to take the dose of IMP at site, after a pre-dose PK sampling. The approximate time of dose administration on the four previous days and time of PK sampling will be recorded in the eCRF.

In case of early discontinuation visit, PK sampling is not required at the withdrawal visit if the subject had no IMP administration the day prior to the withdrawal visit.

Details of blood sampling process, sample handling and shipment are described separately in a laboratory manual provided by the central laboratory.

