11.2 DOSAGE AND ADMINISTRATION

Linzagolix and corresponding placebo treatments will be supplied as film-coated tablets for oral administration and given as monthly treatment kits (Figure 5).

ABT and corresponding placebo will be supplied as red capsules and given as 3-monthly treatment kits.

IMP treatment will start on Day 1 and will be administered once daily up to the day preceding the Month 6 visit. The subjects will have to swallow two tablets of linzagolix/placebo and one capsule of ABT/placebo, ideally at the same time each day.

On the day of a study visit, the subject must take the study medication at site, after the PK blood sample collection, except on Day 1 visit where the study medication must be taken before the PK blood sample collection (at least 1.5 h before). The site staff will record in the eCRF the time of study medication intake. The linzagolix/placebo tablets must be taken from the kits dispensed on that visit (and not from the previously dispensed kits). On Day 1 and Month 3 visits, ABT/placebo capsules must be taken from the kits dispensed during these visits. On Month 1, 2, 4 and 5 visits, ABT/placebo capsules must be taken from the previously dispensed kits.

The treatment groups are described below:

Treatment group	Daily dose Day 1 to Month 6			
	Linzagolix active tablets	Linzagolix placebo tablets	ABT active capsules	ABT placebo capsules
75 mg	1 □ 75 mg	1 □ placebo 200 mg	None	1 capsule
200 mg	1 □ 200 mg	1 □ placebo 75 mg	1 capsule	None
Placebo	None	1 □ placebo 75 mg AND 1 □ placebo 200 mg	None	1 capsule

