Document Version No.:	V5.0	Document Date:	13-JUN-2022

Table

Page

T 1 1 1 0 1		10
Table I Sch	hedule of Assessments – Screening and Treatment Periods	
Table 2 Schedule of	f study assessments - Follow-up Period	
Table 3 Theoretical	l Visit Dates in Main Treatment Period	
Table 4 Theoretical	l Visit Dates in Follow-up	
Table 5 Proposed a	nchors for MCT estimation for each endpoint	
Table 6 List of AT	C codes for analgesics and opioids	64
Table 7 Morphine N	Milligram Equivalents for Narcotic Analgesics	
Table 8 Mapping R	ules for Device	
Table 9 Mapping R	ules for Signant Health Device	

Sponsor:	ObsEva		
Protocol:	18-OBE2109-003		
Document Version No.:	V5.0 Document Date: 13-JUN-2022		

ABBREVIATIONS

Abbreviation	Definition
ABT	Add-back therapy
AE	Adverse events
ALP	Alkaline Phosphatase
ALT	Alanine Aminotransferase
AMH	Anti-Mullerian hormone
AST	Aspartate Aminotransferase
ATC	Anatomic Therapeutic class
AUC	Area under the concentration versus time curve
AUC ₀₋₂₄	Area under the concentration versus time curve from time 0 to the end of the dosing interval 24 hours later, calculated using linear trapezoid rule
BCP	Best Cut Point
BMD	Bone Mineral Density
BMI	Body Mass Index
CDF	Cumulative Distribution Function
CI	Confidence Interval
ClinRO	Clinician Reported Outcome
CM	Concomitant Medication
C _{max}	Maximum plasma concentration
C _{min}	Trough plasma concentration, taken 24 hours after dose and prior to subsequent dose
CSR	Clinical study report
C-SSRS	Columbia-Suicide Severity Rating Scale
CV	Coefficient of Variation
DXA	Dual-energy X-ray absorptiometry
DYS	Dysmenorrhea
E2	Estradiol
EAP	Endometriosis Associated Pain

CRS-BS-TP-000005 V 1.0

Sponsor:	ObsEva		
Protocol:	18-OBE2109-00	3	
Document Version No.:	V5.0	Document Date:	13-JUN-2022

Abbreviation	Definition
ECG	Electrocardiogram
eCRF	Electronic Case Report Form
EHP-30	30-Item Endometriosis Health Profile
ePRO	Electronic Patient Reported Outcome
EQ-5D-5L	EuroQOL 5-Dimension 5-Level
FAS	Full Analysis Set
FSH	Follicle-Stimulating Hormone
FU	Follow-up
GCP	Good Clinical Practice
GGT	Gamma Glutamyl Transferase
GnRH	Gonadotropin releasing hormone
HDL	High-density lipoprotein
HRPQ	Health Related Productivity Questionnaire
HRQoL	Health Related Quality of Life
HRUQ	HealthCare Resource Utilization Questionnaire
ICH	International Conference on Harmonisation
IDMC	Independent Data Monitoring Committee
IMP	Investigational Medicinal Product
INR	International Normalized Ratio
IRB	Investigational Review Board

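### The pre-dose PK rule limits time since last dose at Month 6 only, so off-drug samples at Months 1 to 5 can enter the concentration summaries

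*SAP*

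**What the plan says.** SAP 4.2.9 (Pharmacokinetics data) sets two conditions for a sample after Day 1. First, it was taken before or at that day's dose, or "IMP intake is not done on the day of PK sampling (i.e. considered as pre-dose"). Second, "PK assessment date is within +/-10 days of the theoretical visit and up to 2 days after last IMP intake for Month 6 visit". Samples with a missing sampling time, or with a same-day dose of unknown time, are left out.

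SAP 4.7 summarises the concentrations in the PK Set by arithmetic and geometric mean, SD, CV% and quantiles, with values below the limit of quantification set to zero. The protocol synopsis says the summary is by time point and treatment group.

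On timing, Protocol 5.5.1 reports "a half-life of about 15–20 hours". Protocol 10.5 provides that "The approximate time of dose administration on the four previous days and time of PK sampling will be recorded in the eCRF". In SAP 4.7 those prior-day times appear only in listings. Protocol 11.2 asks for dosing "ideally at the same time each day", without fixing a time of day. Protocol 13.4 leaves the rules for excluding individual data points, including time windows, to the SAP.

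**The concern.** The inclusion rule looks at the day of sampling and at the calendar, but at Months 1 to 5 it never looks back to the previous dose. The 10-day window ties the sample to the theoretical visit date, not to dosing. A woman who last took drug three or five days before her Month 3 sample meets both conditions and is tabulated as a Month 3 pre-dose value. This holds whether or not she then takes a dose on site.

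The documents themselves allow for such gaps. Doses can be missed. Protocol 12.1.1 lists temporary interruption of study drug as an action taken for an adverse event. Protocol 10.7.2.1 and SAP 2.3 have study treatment interrupted at high serum calcium, with a repeat test within 2 weeks. They do not say when drug is resumed, so a visit may or may not fall inside the gap.

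At stake is what the pre-dose tables mean. If off-drug samples are included, the visit means and CV% reflect interruptions as well as dose, and a reader of the table cannot tell the two apart.

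**Working it through.** The plan states no figure that depends on this rule, so there is nothing to reproduce. The check sizes the effect.

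**Inputs.** Half-life 15 to 20 h (Protocol 5.5.1). Reference time 24 h, because dosing is once daily and the SAP's abbreviation list defines Cmin as "Trough plasma concentration, taken 24 hours after dose and prior to subsequent dose". That definition is used only as a benchmark: the inclusion rule says pre-dose, not trough. Mono-exponential decay after absorption and distribution is assumed. The half-life of the metabolite KP017 is not given, so the figures are for linzagolix only.

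**Single samples.** Ratio to the 24 h value = 2^(−(t − 24)/half-life).

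| Hours since last dose | Half-life 15 h | Half-life 20 h | Admitted as pre-dose? |
|---|---|---|---|
| 12 | 2^0.8 = 1.74 | 2^0.6 = 1.52 | all visits |
| 24 | 1.00 | 1.00 | all visits |
| 48 | 2^−1.6 = 0.33 | 2^−1.2 = 0.44 | all visits |
| 72 | 2^−3.2 = 0.11 | 2^−2.4 = 0.19 | Months 1 to 5; Month 6 depends on how 2 days is counted |
| 96 | 2^−4.8 = 0.04 | 2^−3.6 = 0.08 | Months 1 to 5 |
| 120 | 2^−6.4 = 0.012 | 2^−4.8 = 0.036 | Months 1 to 5 |

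At a constant clock time, 72 h corresponds to two missed days before the visit and 120 h to four.

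**Effect on a reported mean.** Let a share f of the samples sit at ratio r and the rest at 1, with the same underlying distribution otherwise. The arithmetic mean is then multiplied by (1 − f) + f·r and the geometric mean by r^f. The documents give no f, so 5%, 10% and 20% are assumptions. For samples at 72 h:

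| f | Arithmetic mean (15 h, 20 h) | Geometric mean (15 h, 20 h) |
|---|---|---|
| 5% | 0.955, 0.959 | 0.895, 0.920 |
| 10% | 0.911, 0.919 | 0.801, 0.847 |
| 20% | 0.822, 0.838 | 0.642, 0.717 |

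So with 10% of samples at 72 h, the arithmetic mean falls by 8 to 9% and the geometric mean by 15 to 20%.

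**Zeros.** A sample far enough off drug to fall below the limit of quantification enters as zero. One zero makes the product, and so the geometric mean, zero. Computed through logarithms, the geometric mean is undefined. The limit itself is not stated, so the time at which this happens cannot be given.

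**Could another rule remove these samples?**
- The PK Set (SAP 3.1) excludes subjects with major deviations affecting PK. It works by subject and names no time-since-dose criterion.
- Protocol 10.5 and SAP 4.2.7 waive PK sampling at a withdrawal visit if no drug was taken the day before. This makes the sample optional; it does not exclude one that was taken, and it does not cover scheduled visits.
- The listings show prior-day dose times but leave the tables unchanged.

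**The case against.** The strongest reply is that little depends on these tables. SAP 2.5.2 calls the PK analyses exploratory, the PK/PD work is reported separately, and no test, power figure or efficacy conclusion uses the means. Visit-day doses are taken on site after sampling, so an off-drug sample is an exception to the design. A limit at Month 6 alone has some logic, because treatment is "administered once daily up to the day preceding the Month 6 visit", while at Months 1 to 5 dosing should be continuing. The rule already screens single samples, and the SAP's change log says the PK windows were added in V3.0 after blinded data review. All of this stands as a limit on importance. None of it supplies the missing limit, and the change log does not say that time since last dose was examined.

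A reader might infer more than the documents support:

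- **A spread of about 42- to 147-fold in the tables.** This is the ratio of a 12 h to a 120 h sample (2^(108/20) and 2^(108/15)). It compares two hypothetical samples and is not an effect on a reported statistic. No frequency of mistimed samples is given.
- **That steady state cannot be judged.** The documents do not say that these tables serve that purpose, and confounding by timing is not the same as being uninformative.
- **That the Day 1 rule is faulty too.** It follows the protocol, which asks for a sample at least 1.5 h after the on-site dose.
- **That only samples near 24 h should count.** A narrow window such as 20 to 28 h would drop women who dose in the evening, as the protocol allows, and it would rely on prior-dose times that Protocol 10.5 calls approximate.

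**Conclusion.** The gap is real and narrow. At Months 1 to 5 the SAP accepts off-drug samples as pre-dose values because it sets no maximum time since last intake, although it sets one at Month 6. A sample at 72 h is expected at about 0.11 to 0.19 of the 24 h value and one at 120 h at about 0.01 to 0.04, given the protocol's half-life and mono-exponential decay. These samples can be averaged into the tables; whether they are, and how often, is not known from the documents. The geometric mean is the more exposed statistic, because of both the very low values and the zeros.

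A separate, milder feature is that no visit has a minimum time since dose. A protocol-compliant evening doser sampled about 12 h later contributes about 1.5 to 1.7 times the 24 h value. That calls for showing the timing, not for excluding her.

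The consequence is confined to exploratory descriptive PK tables.

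**What to change.** In SAP 4.2.9, apply a maximum time since last IMP intake at Months 1 to 5 as well. The 2-day limit already used at Month 6 would do, stated in hours so that it cannot be read as calendar days. A 48 h limit still admits values at 0.33 to 0.44 of the 24 h value, so a tighter pre-specified limit is an option.

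Derive the time from the four prior-day dose times already in the eCRF. If no intake is recorded on any of those days, a sample is beyond a 2-day limit. State how a missing prior-dose time is handled. A limit of this width tolerates approximate dose times far better than a window of a few hours would.

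In SAP 4.7, list excluded samples with their actual time since dose, report the number excluded by visit and arm, and present time since last dose beside the pre-dose summary. Keep all samples for the separate PK/PD modelling.

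The cost is a few lines of SAP text and one derived variable, with slightly fewer samples in the table. If the tables have already been produced, a documented supplementary table serves the same purpose.
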